H1: OxyGeni oxygen delivery system will reduce the likelihood of surgical wound complication including tissue necrosis and its volume, infection, surgical revision, and amputation compare to standard of care dressing.

Aim2: To assess changes in skin perfusion in patients treated with OxyGeni oxygen delivery system.

H2: OxyGeni oxygen delivery system will improve perfusion in >50% of the patients as compared to baseline (measurements at baseline, 2 weeks, and 4 weeks).

Aim3: To evaluate changes in quality of life, anxiety during dressing change, and psychosocial parameters in patients with a surgical wound treated by OxyGeni oxygen delivery system

H3: Oxygen delivery will improve subject quality of life, reduce anxiety, and reduce perceived pain and physiological stress response during dressing change compared to the control group.

Aim4: To assess acceptability, user-friendliness, and Perception of benefit.

H4: OxyGeni oxygen delivery system will be considered to be practical to use, easy to use, and is perceived to be beneficial from both practitioner and subject as assessed by user friendliness questionnaire adapted for the purpose of this study (assessment at the conclusion of the study). This questionnaire is attached to the protocol.

H5. OxyGeni oxygen delivery system therapy will improve scar cosmetic appearance as assessed practitioner using the Scar Cosmesis Assessment and Rating (SCAR) Scale.

This is an exploratory study and our parameters of interest are: ¿ Complete wound healing post surgical intervention. ¿ % of wound complication post-surgical wound closure ¿ Perfusion improvement at 2 weeks, 4 weeks and 6 months compared to baseline and compared to the control group. ¿ Differences in pain, stress, anxiety, and quality of life compared to the control group ¿ Device acceptability and perception of benefit

Section E: Protocol Risks/Subjects

E1. Risk Category

Category 2: Research involving greater than minimal risk, but presenting the prospect of direct benefit to the individual subjects.

E2. Subjects

Gender:

Both

Age:

Adult (18-64 yrs), Geriatric (65+ yrs)

Ethnicity:

All Ethnicities

Primary Language:

English, Spanish

Groups to be recruited will include:

Patients

Which if any of the following vulnerable populations will be recruited as subjects?

Vulnerable populations require special protections. How will you obtain informed consent, protect subject confidentiality, and prevent undue coercion?

E3. Pregnant woman/fetus

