Medical History: The presence of diabetes will be based on American Diabetes Association criteria if applicable. This will include: duration and type of diabetes, type of diabetes medication (insulin, oral, combination therapy, diet), previous history of foot ulcers, amputation (toe, foot), lower extremity bypass, lower extremity angioplasty, Coronary artery bypass surgery, cardiac angioplasty, arthritis, liver disease, osteoporosis, malignancy, and bone tumors. We will use the Kaplan comorbidity index to record disease severity. We will measure height and weight to determine body mass index (BMI). We will evaluate and record glycated hemoglobin, albumin and prealbumin at baseline only in those patient charts where it is available due to the patient's standard of care treatment. Lab results will only be obtained only at the Baseline visit. Please note that patients will be recruited from an existing clinic population where they are already receiving Standard of Care procedures. These results will be obtained from your medical record at screening/baseline visit.

Social Factors: We will evaluate the following factors: marital status, years of education, type of work, tobacco history (pack years, current smoker, current use of chewing tobacco, previous smoker, no tobacco history), drug history (current, previous history, no drug history), and alcohol history. These factors will be collected at screening/baseline visit.

Peripheral Neuropathy: We will use Vibration Perception Threshold (VPT) Testing. VPT will be evaluated at the distal great toe, heel and 5th metatarsal head using a Biothesiometer. (Measurements will be done on screening/baseline visit and visit 4)

Heart Rate Monitoring: Zephyr BioHarness is an FDA approved wearable sensor which monitors physiological signs such as heart rate (electrocardiograph), breathing rate, skin temperature, and physical activity. This device will be comfortable placed on the sternum attached with either with two electrocardiograph (ECG) electrodes or elastic straps for subjects that report sensitive skin. Researchers will attach this device on the subject only for the duration of the visit. (Measurements will be done at all visits).

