Vascular Assessment: We will assess perfusion of the macro-circulation with arterial Doppler studies and micro-circulation with Skin Perfusion Pressure measurements and Ankle Brachial Index (ABI) will be measured on both extremities. Therefore, we will use the SensiLase system (Väsamed) to measure Skin Perfusion Pressure (SPP) in mmHg. The SensiLase is a device that will record the amount of Skin Perfusion Pressure. (Measurements will be done at screening/baseline visit and visits 2 & 4). We will also obtain oxygen tissue saturation images using Kent Camera or HyperView Camera (every visit)

-Ankle-Brachial Index: This test is to measure blood pressure of the ankle and arm while the subject is at rest. (Measurements will be done on screening/baseline visit and visits 2 & 4). Research Staff will: 1. Attach correct sized cuff on ankle and arm 2. Doppler probe will be placed on ankle and arm. 3. Cuffs will be inflated above your blood pressure. 4. The cuffs will deflate 5. Research Staff will document values in the subjects records. 6. Research Staff will remove the cuffs from the subjects ankle and arm.

-Skin Perfusion Pressure: This test will help the physician and researchers know if the tiny blood vessels in the subjects feet are blocked, damaged or if wound are getting enough blood to heal properly. (Measurements will be done on screening/baseline visit and visits 2 & 4) Research Staff will: 1. Ask the subject to lie flat 2. Research staff will place correct

sized pressure cuffs around the subjects ankles. 3. Research staff will also place an adhesive pad along with a sensor as (sensors will not be touching the skin directly) it will measure Skin Perfusion. 4. The cuffs will inflate above systolic blood pressure. 5. Research Staff will document values in the subjects record 6. Research Staff will remove cuffs from the ankle.

Adverse Event Reporting: Research Staff will document and report any study/non study related incident as per institution regulations. (Subjects will be asked on screening/baseline visit and visits 1- 4 and at the optional 5 visit).

Wound Assessment: A digital photo/video and thermal photo of wound will be taken for wound size verification and evaluate the area of inflammation. (Measurement will be performed at every visit). Photo may be taken with digital camera, KENT NIR camera, or eKARE camera.

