Questionnaires: Quality of Life, Frailty Status, Cognitive Assessment, Sleep Quality and Device Acceptability: To evaluate functional status, we will use well accepted and validated general functional assessment instruments, Promise Global for Quality of Life, Sleep Quality questionnaire (PSQI), TSFI for frailty status, MOCA for Mental Exam. (All questionnaires will be done on screening/baseline visit and visit 4. MOCA will only be done at baseline/screening visit). At the visit 5 (optional) follow-up visit SCAR assessment (the Scar Cosmesis Assessment and Rating Scale), Patient and Observer Scar Assessment Scale (POSAS), and Patient Attitude to Scarring Scale (PASS). Questionnaires may be collected in person or in RedCap.

Dressing Change: All patients will have their dressing changed weekly (screening/initial visit and visits 1-4), the intervention group will be treated continuously with oxygen from the OxyGeni device.

Prior to application of the OxyGeni, the research staff will: 1. Select a dressing that will cover the wound. 2. Apply absorbent wound padding (e.g. calcium alginate) 3. Place and steri-strip cannula on top of padding. 4. Apply additional padding on top of cannula 5. Wrap dressing as directed by physician.

We may also use an oxygen delivery dressing named Oxyspur instead of traditional dressing based on the judgment of the surgeon. This may facilitate delivery of oxygen to the incision site or wound bed as well as ease of dressing.

Device Acceptability Questionnaire: The subject will be handed a questionnaire to evaluate the study device and provide feedback to the research team. (Visit 4)

SCAR assessment scale will be done to assess the appearance of the scar. In addition, a digital photography will be taken (Visit 5). If the patient is unable to attend, the visit can be done remotely.

Upper Extremity Test: Investigators will measure arm motion from each participant by implementing a validated technology based on wearable sensor system named LegSys. This system will assess respectively spatio-temporal parameters of arm motion in a clinical setting. The LegSys system will be used with 2 sensors to capture arm motion, one placed at the subject's wrist and another at their elbow. While being at a comfortable position, the subject will be asked to flex and extend their arm for 20 seconds at a fast speed. Subject will also be asked to repeat this task but counting backwards as they flex and extend their arm (dual task).

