Pain Intensity Assessment (VAS): The subject will be provided with a numeric pain scale where he/she will report pain intensity. Research staff will document subject's pain level. (Measurements will be done at every visit)

WIFI wound classification (Wound, Ischemia, and foot infection): Podiatric (foot) physician will evaluate the health and wellness of the subject's feet in compliance of standard of care. (Will be done on screening/baseline visit and visit 4)

Screening/Baseline Visit *duration of visit 90 minutes This visit research staff will perform as described above: Medical History, Questionnaires (Pain, Social Factors, and Quality of Life, Sleep Quality, Cognitive Assessment, Frailty), Upper Extremity Test, Peripheral Neuropathy, Heart Rate Monitoring, Vascular Assessment, Wound Assessment, Wound Monitoring, Wifi Wound Classification, Dressing Change and Device Education.

Visit 1, One Week Later *duration 50 minutes This visit research staff will perform as described above: Pain Questionnaire, Heart Rate Monitoring, Adverse Event Reporting, Wound Assessment, Dressing Change and Device Education.

Visit 2, Two Weeks Later *duration of visit 80 minutes This visit research staff will perform as described above: Pain Questionnaire, Vascular Assessments, Heart Rate Monitoring, Adverse Event Reporting, Wound Monitoring, Wound Assessment, Dressing Change and Device Education.

Visit 3, Three Weeks Later *duration 60 minutes This visit research staff will perform as described above: Pain Questionnaire, Heart Rate Monitoring, Adverse Event Reporting, Wound Assessment, Dressing Change and Device Education.

Visit 4, Four Weeks Later *duration of visit 80 minutes This visit research staff will perform as described above: Questionnaires (Quality of Life, Acceptability, Pain, Frailty, Sleep Quality), Vascular Assessments, Heart Rate Monitoring, Adverse Event Reporting, Wound Monitoring, Wound Assessment, Dressing Change.

Visit 5, at a minimum of 6 months after surgery. This visit research staff will perform the SCAR assessment scale, POSAS,

and PASS questionnaires and take a digital picture of the scar. If the patient is unable to attend, the visit can be done remotely.

Section G: Sample Size/Data Analysis

G1. Sample Size

How many subjects (or specimens, or charts) will be used in this study?

Local: 60 Worldwide: 60

Please indicate why you chose the sample size proposed:

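### H3 concerns pain and physiological stress during dressing change, but nothing in the supplied text ties either measure to the dressing change

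*Combined protocol and SAP*

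**What the plan says.** **Hypothesis (Section D, Aim 3 and H3).** H3 states that oxygen delivery will "reduce perceived pain and physiological stress response during dressing change compared to the control group". Aim 3 sets the same moment for anxiety: "anxiety during dressing change, and psychosocial parameters in patients with a surgical wound".

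**Pain (F2, Pain Intensity Assessment).** "The subject will be provided with a numeric pain scale where he/she will report pain intensity". The frequency follows: "Research staff will document subject's pain level. (Measurements will be done at every visit". No moment within the visit and no reference period is given. The task is headed VAS but described as a numeric scale.

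**Physiological signals (F2, Heart Rate Monitoring).** The wearable sensor "monitors physiological signs such as heart rate (electrocardiograph), breathing rate, skin temperature, and physical activity". On timing: "Researchers will attach this device on the subject only for the duration of the visit. (Measurements will be done at all visits". No event marker, resting period or derived stress variable is described.

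**Dressing change (F2, Dressing Change).** Dressings are changed at the screening/initial visit and at Visits 1-4. The listed steps include no pain rating, time stamp or sensor mark.

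**Visit lists (end of F2).** Pain and dressing change appear as separate items. The visits last 90 minutes at baseline, then 50, 80, 60 and 80 minutes at Visits 1 to 4.

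**Analysis (G2).** Pain, anxiety and stress are secondary outcomes, compared between groups by a univariate general linear model. The dressing-change qualifier is absent. No sensor summary, time window or visit is named.

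**The concern.** The dressing change is the substance of this part of H3. The prediction is about the response to one event, and is not a claim about pain or heart rate over a clinic visit in general. A test of it needs a pain score that refers to that event and a sensor segment that belongs to it. The plan provides for neither.

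The gap cannot be dependably closed after data collection. A trace without start and end times cannot be reliably cut to the dressing change, and a pain score given at an unknown point in the visit cannot be assigned to it later. A null result on pain or stress could then not be read as evidence against H3, and a positive one could not be attributed to the dressing change. G1 says a later trial will be designed from this pilot, so data that cannot be interpreted would carry forward.

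**Working it through.** The plan gives no effect size, standard deviation or power for pain or stress, so there is no figure to reproduce. The check is mainly a comparison of texts.

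**1. Hypothesis against measurement**

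| Element | H3 | F2 | G2 |
|---|---|---|---|
| Pain | during dressing change | reported at each visit, moment unstated | pain, no time restriction |
| Stress | during dressing change | whole-visit trace, no marker, no rest reference | stress, no variable or window |
| Visit analysed | not stated | all visits measured | not stated |

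The restriction in the first column has no counterpart in the other two.

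**2. Is the dressing change inside the recording?** Yes. Dressings are changed at baseline and Visits 1-4, and the sensor is worn throughout each visit. The raw signal exists. The time marks and the outcome definition do not.

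**3. What a whole-visit mean would retain.** This is an illustration only, since G2 names no summary. Assume that the dressing change takes *m* = 5 to 15 minutes (not in the documents) and that the arms differ only in that window. The share retained is *m*/*T*, where *T* is the visit length in F2.

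| *T* (min) | *m* = 5 | *m* = 15 |
|---|---|---|
| 50 (Visit 1) | 5/50 = 10% | 15/50 = 30% |
| 60 (Visit 3) | 5/60 = 8% | 15/60 = 25% |
| 80 (Visits 2 and 4) | 5/80 = 6% | 15/80 = 19% |
| 90 (baseline) | 5/90 = 6% | 15/90 = 17% |

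An assumed 10 bpm difference in the window would appear as 10 × 5/90 = 0.6 bpm to 10 × 15/50 = 3.0 bpm.

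**4. Effect on power under the same condition.** Take 30 per arm, two-sided alpha 0.05, an assumed standardised difference *d* = 0.8 in the window, and an unchanged standard deviation. By the normal approximation, power is Φ(*d*√(30/2) − 1.96).

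- In the window: Φ(0.8 × 3.873 − 1.96) = Φ(1.138) = 87%.
- Retaining 30%: *d* = 0.24, Φ(0.930 − 1.96) = 15%.
- Retaining 5.6%: *d* = 0.044, Φ(0.172 − 1.96) = 4%.

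**5. Other tasks in the visit.** In the Skin Perfusion Pressure test, "The cuffs will inflate above systolic blood pressure"; this is done at baseline and Visits 2 and 4. In the Upper Extremity Test, "the subject will be asked to flex and extend their arm for 20 seconds at a fast speed", with a repeat as a dual task; among baseline and Visits 1-4 it is listed only at baseline. If the repeat also lasts 20 seconds, the arm test takes 40/5,400 seconds = 0.7% of the 90-minute visit. Both tasks apply to both arms. They add noise, but do not by themselves favour one arm.

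**The case against.** The strongest reply is that the sensor does record the dressing change, so the data are not lost. That is correct. A reader might infer that the measures miss the hypothesised response altogether; the documents do not support that. What stands is that F2 requires no mark by which the segment could be found.

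Other stronger readings also go too far:

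- **That pain is rated exactly once per visit.** The text gives the visits, not the number of ratings. Each visit list shows pain once, but states no order of tasks. A rating at the dressing change is neither required nor excluded.
- **That a true effect will be diluted away.** This presumes a whole-visit mean, which G2 does not specify. Even then, up to 30% would remain under the assumptions above.
- **That the cuff and arm tests bias the comparison.** The task lists are the same for both arms, and H3 compares arms. A task mix that changes between visits adds noise to change from baseline, but does not distort a comparison of arms at the same visit.

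Table 1, which F1 says summarises the key measurements by visit, is an attachment that was not available. Timing detail there cannot be excluded, though G2 would still need to define the outcomes.

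Finally, this is a self-described exploratory pilot, the outcomes are secondary and unpowered, and the primary outcome is unaffected. That limits the weight of the point but does not answer it.

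**Conclusion.** The point holds in this form: in the supplied text, H3's pain and stress outcomes are not defined relative to the dressing change, so the plan as written cannot test that part of H3. The finding rests on comparing Section D with F2 and G2, and is subject to what Table 1 may contain.

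The size is conditional. The 6-30% retention depends on an assumed 5-15 minute dressing change, an effect confined to it, and use of a whole-visit mean. The power figures also assume a standardised difference of 0.8 and an unchanged standard deviation. No comparable figure can be given for pain, because an untimed score may or may not reflect the dressing change.

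The change should be made before further data are collected, because it alters what is recorded. It does not affect the validity of the primary comparison.

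**What to change.** **In F2, at baseline and Visits 1-4:**

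- Take one pain rating just before the dressing is removed and one immediately after the change, on a single named 0-10 numeric scale. This also settles the VAS/numeric labelling.
- Log the start and end time of the dressing change.
- Add a few minutes of seated rest with the sensor on, just before the change. F2 has no such period now.
- Keep the cuff and arm tests outside the rest and dressing-change window.

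**In G2:**

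- Define the stress outcome as mean heart rate in the dressing-change window minus mean heart rate in the preceding rest.
- Define the pain outcome as the post-change rating, with the pre-change rating as covariate.
- Name the visit analysed, for example Visit 4 or the mean of attended Visits 1-4. Either gives one value per subject, as a univariate model needs. The choice should be made in advance, because F1 lets the weekly visits end early on healing or surgical revision.

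If Table 1 already sets these timings, carry them into F2 and G2.

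**Cost:** one extra rating, two time stamps and a few minutes of rest per visit, plus some care over task order. No new device or staff is needed; the sensor recording is already planned.

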Will pregnant women and/or fetuses (as described in 45 CFR 46 Subpart B) be enrolled in the research? No

E4. Neonates

Will neonates of uncertain viability or nonviable neonates (as described in 45 CFR 46 Subpart B) be enrolled in the research?

E5. Children

Will children be enrolled in the research?

Section F: Design/Procedure

F1. Design

Select one category that most adequately describes your research:

c) Pilot

Discuss the research design including but not limited to such issues as: probability of group assignment, potential for subject to be randomized to placebo group, use of control subjects, etc.

This study will be a 4 weeks prospective (or up to wound healing or surgical revision, whichever came first), experimental study with N=60 consecutive patients, who are undergoing surgical closure.

Subjects will be randomized to either control or intervention group. The intervention group will receive the OxyGeni device and place the oxygen delivery within SOC dressing. The control group will receive standard of care wound dressing.

All patients will have baseline assessment including visual, dermal, neuropathy (Vibration Perception Threshold) and vascular assessment (ABI and Skin Perfusion Pressure). Then, the status of wound closure and presence of wound complication will be monitored every week. Each subjects will need up to 5 visits including baseline assessment, and weekly assessment up to 4 weeks or full wound healing or surgical revision, whichever came first, and an additional follow-up visit at a minimum 6 months after the surgery. At each visit, patients will be provided standard of care treatment including physical assessment, debridement and offloading. Table 1 in attachments' section summarizes the key measurement at each study visit.

Please note that no screening activities will take place prior to the patient signing a consent form.

Inclusion Criteria:

18-85 years of age. Ability to provide informed consent. Presence of a wound due to surgical intervention and closure. Subject or responsible caregiver is willing and able to maintain the required offloading (as applicable for the location of the wound) and applicable dressing changes

Exclusion Criteria:

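### If weekly assessment stops at healing or revision, early stoppers lack week-4 perfusion and quality-of-life values, and an undated primary outcome is observed for unequal time

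*Combined protocol and SAP*

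**What the plan says.** **Early stop.** F1 states the rule twice. The study is "4 weeks prospective (or up to wound healing or surgical revision, whichever came first", and each subject has "weekly assessment up to 4 weeks or full wound healing or surgical revision, whichever came first". F1 also sets a ceiling of five visits, adds a follow-up visit at least six months after surgery, says complications are looked for at the weekly monitoring, and refers to a Table 1 in the attachments, which is not in the text available here.

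**Visit schedule without a stopping condition.** In F2:
- Vascular assessment: "Measurements will be done at screening/baseline visit and visits 2 & 4".
- Adverse events: "Subjects will be asked on screening/baseline visit and visits 1- 4 and at the optional 5 visit".
- Dressing change: "All patients will have their dressing changed weekly (screening/initial visit and visits 1-4".
- Questionnaires: "All questionnaires will be done on screening/baseline visit and visit 4".
- Device acceptability: "The subject will be handed a questionnaire to evaluate the study device and provide feedback to the research team. (Visit 4".

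The visit list then places Visit 4 at four weeks, unconditionally.

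**Primary outcome.** G2 names the percentage of wound complications after surgery, compared by chi-square. It gives no time point and no rule for patients whose assessment ended early.

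**Later contacts.** F2 provides a phone call up to three months after the last visit and a billing-record review to explore costs. Section K includes health-record information in the research data. Visit 5 is described inconsistently: F1 and the F2 visit list give it without calling it optional, whereas other parts of F2, J2 and Section L call it optional. None of these contacts is tied to the primary outcome.

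**The concern.** Two consequences follow if the F1 rule is applied as written.

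1. **Week-4 secondary outcomes.** Quality of life is collected only at baseline and Visit 4, and skin perfusion pressure only at baseline and Visits 2 and 4. A patient whose assessment ends by Visit 3 has no week-4 value for either. Healing and revision occur after randomisation and may depend on treatment, so the remaining patients need not be comparable between arms. The direction of that selection is unknown. This problem does not depend on any assumption about complications after healing.
2. **Primary outcome.** Ending weekly assessment ends the planned search for complications. The background text suggests that the device could speed epithelialization. If it does, device patients would be watched for less time, and part of any lower complication rate could reflect that.

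G1 says the pilot will feed the power calculation for a later trial. A complication rate with no defined window is a weak input to that.

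**Working it through.** The plan gives no figure for this point to reproduce. It gives no healing times and no complication risk after healing, so the primary-outcome bias cannot be computed from it. What follows is a reading of the schedule and then an illustration on stated assumptions.

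**Which outcomes are affected under the F1 rule**
- Quality of life (H3) and skin perfusion pressure (H2): no week-4 value if stopped by Visit 3, though a Visit 2 perfusion reading may exist.
- Patients first judged healed at Visit 4 are assessed at that visit and are not lost.
- Pain, heart rate and oxygen imaging: taken at every visit, so only partly affected.
- Device acceptability (H4): scheduled at Visit 4, but H4 places it at the conclusion of the study, so it might be collected at exit.

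**Inputs for the illustration**
- From G1: control risk R = 20% to 30%, taken here as a 4-week risk; 30 patients per arm.
- Assumed: constant weekly hazard; no device effect on complications; healed patients stop at week w; the arms differ by g in the share of event-free patients who stop as healed; the hazard after healing is k times the earlier one.

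**Formulas**
- Weekly hazard: h = 1 − (1 − R)^(1/4).
- Risk by week w: r_w = 1 − (1 − h)^w.
- Spurious difference = (1 − r_w) × g × [1 − (1 − kh)^(4 − w)].

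**Worked case**, R = 0.30, w = 2, g = 0.50: h = 0.0853 and r_2 = 0.1633.
- k = 1: 0.8367 × 0.50 × 0.1633 = 0.0683, or 6.8 points (2.05 patients of 30).
- k = 0.25: 0.8367 × 0.50 × [1 − (1 − 0.0213)^2] = 0.8367 × 0.50 × 0.0422 = 0.0177, or 1.8 points.

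**Stopping at week 2: spurious difference in points, R = 20% to R = 30%**

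| Gap in share healed | k = 1 | k = 0.5 | k = 0.25 | k = 0 |
|---|---|---|---|---|
| 10 points | 0.94–1.37 | 0.48–0.70 | 0.24–0.35 | 0 |
| 25 points | 2.36–3.42 | 1.20–1.75 | 0.60–0.88 | 0 |
| 50 points | 4.72–6.83 | 2.39–3.49 | 1.21–1.77 | 0 |

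One patient of 30 is 3.3 points. With R = 25% included, the grid has 36 cells. Five exceed one patient, and four of those assume unchanged risk.

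**Other stopping weeks**, g = 0.50 and k = 1: week 3 gives 2.29 to 3.26 points, about half; week 1 gives 7.29 to 10.73, about 55% more.

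**Loss from Visit 4.** For each 10% of an arm's event-free patients healed by week 2, the number absent is 30 × (1 − r_2) × 0.1. That is 2.68 at R = 20% and 2.51 at R = 30%.

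**Stopping at revision.** Revision is itself a listed complication. A patient who stops there has already had an event, so an endpoint that counts each patient once loses nothing.

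**The case against.** **The schedule may not contradict itself.** A reader might infer a flat contradiction between F1 and F2. The text does not establish that. The ceiling of five visits in F1 allows the F2 list to be read as what happens at each visit if it takes place, and Table 1 may settle the matter. This stands: the gap is an unresolved ambiguity. It does not remove the concern, because that reading is exactly the one under which early stoppers lose their week-4 data.

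**A window is implied.** F1 describes a 4-week study with weekly complication monitoring. That is a fair reading, but G2 does not adopt it, and F1 shortens the period for healed patients.

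**The design does not necessarily create an apparent benefit.** A reader might infer that it does. A high-end illustration shows how: with a true 4-week risk of 25% in both arms, weekly healing of 10% versus 30%, and hazard unchanged after healing, observed risks are 21.7% and 16.3%. Over true risks of 20% to 30%, a two-sided chi-square then rejects in 7.8% to 8.8% of trials. The documents do not support so strong a conclusion. G1 describes the control event as wounds failing to close, and the background says necrosis delays healing. Both suggest that healing and the event are largely alternatives, so risk after healing would be low. The documents do not address infection, dehiscence or revision after healing, and the visible text does not define full healing. The statement on faster epithelialization is itself tentative, and it is offered as the route to less necrosis. A large healing gap with no effect on complications is therefore an artificial case.

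**Late events may surface elsewhere.** The phone call, Visit 5 and the health and billing records could reveal some. True, but none is assigned to the primary outcome.

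**This is an exploratory pilot.** That limits the severity. It does not remove the need for a dated outcome.

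**Conclusion.** The point holds in a limited form and should be fixed. The firmer part concerns the secondary outcomes: under the F1 rule, patients healed or revised by Visit 3 have no scheduled week-4 perfusion or quality-of-life value. About 2.5 to 2.7 of an arm's 30 patients would be lost from Visit 4 for each 10% of event-free patients healed by week 2.

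For the primary outcome, the bias is zero if no complication follows healing and probably small otherwise. With stopping at week 2 it is at most about 2 points at a quarter of the earlier risk. It reaches 4.7 to 6.8 points only with unchanged risk and a 50-point healing gap. G1 plans a reduction from 20–30% to below 5%, a difference of at least 15 to 25 points, and its wording on the event points to the low end of the bias. All these sizes rest on assumed healing patterns and a constant hazard. Confidence is medium, because Table 1 is not visible and may already resolve the schedule.

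**What to change.** **In F1**, reconcile the early-stop sentences with the F2 schedule. Suggested sense: complication status, the week-4 questionnaires and, where feasible, perfusion are collected to week 4 for every randomised patient whatever the wound status. State that this concerns data collection only and does not alter dressing, debridement, offloading or device use, since F1 and F2 attach care to the same visits. The means already exist: the scheduled visits, the home visits in F2, and remote forms ("Questionnaires may be collected in person or in RedCap"). State whether perfusion can be measured at home, because the text does not say. If Table 1 already keeps Visit 4 or an exit assessment after healing, say so in F1.

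**In G2**, define the primary outcome as the proportion of randomised patients with at least one listed complication within 4 weeks of baseline, each counted once in the assigned group. State whether dehiscence counts: the background names it and H1 does not. Report amputation after a revision descriptively, since a once-per-patient endpoint will not show it.

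**Cost.** Low but not nil. The $450 in Section L equals 6 × $75, so Visits 1 to 4 are already budgeted. A patient who would have stopped at Visit 2 makes two more visits: 2 × $75 = $150 and 60 + 80 = 140 minutes. One who would have stopped at Visit 1 makes three: 3 × $75 = $225 and 80 + 60 + 80 = 220 minutes. Some healed or revised patients therefore return for visits they could have skipped. Section L bills wound care and post-operative visits to insurance at visits 0, 2 and 4; some Visit 4 items may not be billable as standard care for a healed patient and could fall to the study.
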